### 7.4.1 Primary Hypothesized Endpoints

#### Safety

The primary safety endpoint is the occurrence of Primary Adverse Events (PAEs) (within seven (7) days of the index ablation procedure where the investigational OMNYPULSE™ Catheter and TRUPULSE™ Generator are used per clinical investigation plan).

PAEs include the following Adverse Events (AEs):

Atrio-Esophageal Fistula*	Phrenic Nerve Paralysis
Cardiac Tamponade/perforation**	Pulmonary Vein Stenosis*
Device or procedure related death*	Stroke/Cerebrovascular Accident (CVA)
Major Vascular Access Complication/Bleeding	Thromboembolism
Myocardial Infarction	Transient Ischemic Attack (TIA)
Pericarditis	Heart Block
Pulmonary Edema (Respiratory Insufficiency)	Vagal Nerve injury/Gastroparesis

\*Device or procedure related death, pulmonary vein stenosis and atrio-esophageal fistula that occur greater than one week (7 days) and less than or equal to 90 days post-procedure are considered and analyzed as PAEs.

\*\* Cardiac Tamponade/Perforation occurring up to 30 days post AF ablation process procedure will be considered a PAE.

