### 13.5 Post-Ablation Follow-up Schedule

The subjects will be required to complete follow-up visits through 12 months post index ablation procedure. Follow-up will be done at 7 days (phone call or clinic visit), 1, 3, 6 and 12 months (clinic visit). Follow-up visits should be scheduled according to the following timeframes: 1 month (1M 23-37), 3 months (3M, day 76-104), 6 months (6M, day 166-194) and 12 months (12M, day 335-379). Follow-up visit schedule should be based on the date of the index ablation procedure and will not reset if subject undergoes a repeat AF ablation procedure.

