### 13.5.2 Monthly follow-up visit

At 1, 3, 6 and, 12-month follow-up visits, the following assessments will be performed:

- **Medical evaluation:**
  - AEs
  - Cardiac and anti-coagulation medication regimen
  - Cardiac related hospitalization and cardioversions
  - 12 Lead-ECG
  
- **As from 1-month: Atrial arrhythmia monitoring (non-SOC)**
  - **Remote Monitoring:** subjects will be provided with a remote monitoring device at the 1M FU visit and asked to record and transmit a minimum of 1 transmission ( $\geq 30$  seconds) every week through the end of the month 5 of FU. Starting at month 6 of FU, subjects will be asked to record and transmit a minimum of 1 transmission ( $\geq 30$  seconds) every month until the effectiveness evaluation period is completed (12 months post index ablation procedure). Subjects will also be asked to transmit any symptom-triggered episode that occurs from the time they receive the remote monitoring device through the 12M FU visit. Remote monitoring will be **conducted as follows:**
    - Distribution and start by month 1.
    - $<6M$ : Weekly transmission of at least 1 scheduled recording.
    - $\geq 6M$ : Monthly transmission of at least 1 scheduled recording.
    - Conduct and transmit recording whenever symptoms are present.
  - **24 Hour Holter Monitoring:** per CIP a Holter monitor will be used at the 3-, 6- and 12-months follow-up visit to monitor the subjects 'heart rhythm for 24 hours continuously. Following the 24h Holter, subjects will be contacted by the site to verify if symptoms are experienced during 24h Holter. An independent core laboratory will be used to evaluate and assess the remote and 24h Holter monitoring tracings.
  
- Additional Assessments for Cardiac **CT/MRA** subset subjects: A **cardiac CT/MRA** is required to be performed at the 3M FU (non-SOC) visit or any other point in time when the subject presents with symptoms of PV stenosis. For other subjects, a cardiac CT/MRA is only required to be performed if the subject presents with symptoms of PV stenosis.
  
- Additional Assessments for **NA** subset subjects (non-SOC): A **Cerebral MRI, Neurological Exam and Neurological Evaluation using the MMSE, NIHSS and mRS** are required to be performed if any neurological symptoms and/or cerebral ischemic lesions were identified at a prior evaluation. NOTE: Patient questionnaires will only be used in countries with validated languages.
  

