4. Imaging within 6 months prior to procedure to assess the LA and LVEF, in case the imaging assessment is older than 6 months, LA/LVEF dimensions shall be re-measured during the index ablation procedure prior to insertion of the study catheter.
5. Performed the day before procedure or day of ablation procedure to rule out the presence of atrial thrombus using one of the following modalities TEE, ICE, CT, MRI.
6. Data from 12-lead ECG recordings will be collected (For pre-procedure, can be performed before ICF signature. For pre-discharge it is per SOC). Discharged subjects will receive a telephone call or have a clinic visit at 7 days (day 7-9). If subject is coming for a clinical visit at day 7, data from 12 lead ECG will be collected.
7. Arrhythmia monitoring via remote monitoring once per week as from 1-month follow-up visit to the end of 5-month follow-up and monthly as of 6-month follow-up visit and whenever subject feels symptoms.
8. Arrhythmia monitoring via 24H Holter, site to contact subject and verify if any symptoms experienced during the Holter monitoring.
9. Information on any repeat ablation after the index ablation procedure will be collected.
10. Concomitant medication: only cardiac (i.e., anti-arrhythmia drugs, anticoagulation regimen) & index ablation procedure related (i.e., adenosine, anticoagulation (e.g., heparin, pain medication)

11. AEs must be collected from the time the subject signs the informed consent onward.
12. Patient questionnaires will only be used in countries with validated languages.
13. For all subjects: CT/MRA to be completed within 6 months prior to the index ablation procedure. Post procedure: for CT/MRA subset to be repeated at 3M FU, for all subjects CT/MRA to be repeated post procedure in case subject presents with PV stenosis symptoms.
14. For PV Durability subset: an electro anatomical map, activation and voltage map is to be performed during the index ablation procedure (pre and post ablation) and to be repeated at 75 days post procedure (+/- 15 days).
15. For Endoscopy subset: Endoscopy preferable between 1 day to 3 days (72hours) post procedure. For procedures on Friday a window of a maximum of 96 hours is justified.
16. If observations are noted on the post-procedure MRI, the subject must have follow-up MRI at the next follow-up visit(s) until observations are resolved.

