Stroke/Cerebrovascular Accident (CVA)	
Diagnosis:
 
 
-Rapid onset of a focal or global neurological deficit with at least one of the following: change in level of consciousness, hemiplegia, hemiparesis, numbness or sensory loss affecting one side of the body, dysphasia or aphasia, hemianopia, amaurosis fugax, or other neurological signs or symptoms consistent with stroke.
 
-Duration of a focal or global neurological deficit <math>\geq 24</math> h; or <math>< 24</math> h, if therapeutic intervention(s) were performed (e.g., thrombolytic therapy or intracranial angioplasty); OR available neuroimaging documents a new hemorrhage or infarct; or the neurological deficit results in death.
 
-No other readily identifiable non-stroke cause for the clinical presentation (e.g., brain tumor, trauma, infection, hypoglycemia, peripheral lesion, pharmacological influences).
 
-Confirmation of the diagnosis by at least one of the following: Neurology or neurosurgical specialist; Neuroimaging procedure (MR or CT scan or cerebral angiography); Lumbar puncture (i.e., spinal fluid analysis diagnostic of intracranial hemorrhage).
 
 
Definition: Stroke: (diagnosis as above, preferably with positive neuroimaging study)
 
 
Minor—Modified Rankin score <math>< 2</math> at 30 and 90 days
 
Major—Modified Rankin score <math>\geq 2</math> at 30 and 90 days
 

Transient Ischemic Attack	New focal neurological deficit with rapid symptom resolution (usually 1 to 2 h), always within 24h; neuroimaging without tissue injury.
Phrenic Nerve Paralysis (PNP)	Absent phrenic nerve function as assessed by a sniff test. Under this CIP, diaphragmatic paralysis/phrenic nerve palsy will be considered a Primary AE if specified symptoms have not improved and phrenic nerve function is confirmed to be absent by a sniff test at the 3-month visit. This reported PAE, is considered to be permanent when it is still documented to be present 12 months or longer following ablation.
Pulmonary Vein Stenosis 	A reduction of the diameter of a PV or PV branch. Severe PV stenosis ( $\geq 70\%$ reduction in the diameter of the PV) will be considered a PAE and major complication of AF ablation.

Primary Adverse Event	Description / Criteria

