Major Vascular Access Complication /Bleeding	
Major Vascular Access Complication: Development of a hematoma, an AV fistula or a pseudoaneurysm which requires intervention, such as surgical repair or transfusion, prolongs the hospital stay, or requires hospital admission.
 
Major Bleeding: Requires and/or treated with transfusion or results in a 20% or greater fall in hematocrit.

Pericarditis	Pericarditis should be considered a major complication following ablation if it results in an effusion that leads to hemodynamic compromise or requires pericardiocentesis, prolongs hospitalization by more than 48 hours, requires hospitalization, or persists for more than 30 days following the ablation procedure.
Heart Block	Impairment of AV conduction requiring intervention (e.g., temporary, or permanent pacemaker) due to iatrogenic cause (e.g., inappropriate energy application, traumatic maneuvering of catheter or other intracardiac devices)
Pulmonary Edema (Respiratory Insufficiency)	
Respiratory insufficiency resulting in pulmonary complications necessitating intubation or other significant intervention (including diuretics administered specifically for treating pulmonary edema or ICU hospitalization requiring oxygen administration but not intubation). Exclusion criteria include:
 
 
• Pneumonia – infiltrate, fever, and leukocytosis
 
• Acute Respiratory Distress Syndrome
 

Vagal Nerve Injury/ Gastroparesis	Injury to the vagal nerve that results in esophageal dysmotility or gastroparesis. Vagal nerve injury is considered to be a major complication if it requires or prolongs hospitalization  , or results in ongoing symptoms for more than 30 days following an ablation procedure.

 Device or procedure related death, atrio-esophageal fistula and pulmonary vein stenosis that occur greater than one week (7 days) and less than or equal to 90 days post-procedure are considered and analyzed as Primary AE.

 Hemodynamic compromise or instability is defined as Systolic blood pressure < 80 mmHg.

 Patients with non-focal global encephalopathy will not be reported as a stroke without unequivocal evidence based upon neuroimaging studies.

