The main study will enroll 135 evaluable subjects who have symptomatic PAF and are candidates for atrial fibrillation ablation. To minimize the learning curve effect on the evaluation of safety and effectiveness of the OMNYPULSE™ Bi-Directional Catheter, up to 50 Roll-In subjects will be enrolled in the study. These subjects will not be counted in the main study, and data for Roll-In subjects will be analyzed separately from the main study.

During the study, all subjects will be followed for 12 months after index procedure. All subjects will be evaluated at 7 days (Day 7-9), 1 month (Day 23-37), 3 months (Day 76-104), 6 months (Day 166-194), and 12 months (Day 335-379) following the index ablation procedure (Day 0).

The primary safety and effectiveness endpoint will be evaluated using the data available at the time of the 3-month follow-up. The hypothesis testing of the primary endpoints will be performed when all subjects complete their 3-month follow-up. A Clinical Study Report (hereinafter, 3-Month CSR) will be submitted as part of the CE mark application dossier.

After the 3-Month CSR submission, the primary safety and primary effectiveness endpoints, along with associated sensitivity analyses, may be summarized descriptively using the complete follow-up data, if there are any updates on the primary endpoint outcome data. No hypothesis testing will be conducted for the primary endpoints in the final CSR.

Regarding all other study endpoints, they will be summarized descriptively using the full follow-up data. The final analysis results will be compiled and presented in the Final CSR (hereinafter, Final CSR).

Embedded within the main study, there will be a Neurological Assessment (NA) subset, a cardiac Computed Tomography (CT) or Magnetic Resonance Angiogram (MRA) image subset, an Esophageal Endoscopy (EE) subset, and a Pulmonary Vein Isolation (PVI) durability subset. These subsets are intended to delineate safety and assess lesion durability 2-3 months following ablation. Each subset will consist of 30 subjects. The same subjects may participate in all four (4) subsets.

2 Treatment Assignment

This is a single-arm study. All subjects will be treated with the OMNYPULSE™ Bi-Directional Catheter (D-1430-05-SI) and the TRUPULSE™ Generator (D-1417-01-IC), along with any related components and accessories needed for the ablation procedure.

3 Randomization and Blinding Procedures

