7.4 Endpoints and Associated Hypotheses

7.4.1 Primary Safety Endpoint

The primary safety endpoint is the occurrence of primary adverse events (PAEs) within 7 days of the index ablation procedure with the OMNYPULSE™ Catheter and TRUPULSE™ generator, except device or procedure related death, pulmonary vein (PV) stenosis, and atrio-esophageal fistula, which may also be considered as primary adverse event if occurring greater than one week (7 days) and less than or equal to 90 days post-procedure (section 7.4.1 in the Protocol). Cardiac Tamponade/Perforation occurring up to 30 days post AF ablation process procedure will also be considered a PAE (section 7.4.1 in the Protocol). The PAE rate will be compared against a performance goal of 12%.

The hypotheses to be tested for this evaluation are:

$$H_0: P_S \geq 0.12 \text{ vs. } H_A: P_S < 0.12,$$

where P_S denotes the rate of early onset primary adverse events.

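### Does a severe pulmonary vein stenosis first seen on a compliant 3-month scan after Day 90 escape the primary safety count?

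*SAP*

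**What the plan says.** Protocol 7.4.1 extends the 7-day PAE window for three events. It covers device- or procedure-related death together with "pulmonary vein stenosis and atrio-esophageal fistula that occur greater than one week (7 days) and less than or equal to 90 days post-procedure". Note 1 to protocol Table 5 repeats the limit, and SAP 7.4.1 carries it over as "greater than one week (7 days) and less than or equal to 90 days post-procedure", with a reference to protocol 7.4.1. In Table 5 a stenosis qualifies when it is severe (at least 70%): such a "reduction in the diameter of the PV) will be considered a PAE and major complication of AF ablation". That row gives no dating rule.

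All subjects have a baseline CT/MRA. Footnote 13 to protocol Table 4 provides "for CT/MRA subset to be repeated at 3M FU", with no narrower scan window, and protocol 7.3.3 sets the subset at 30 subjects. Protocol 13.5.2 adds: "For other subjects, a cardiac CT/MRA is only required to be performed if the subject presents with symptoms of PV stenosis". The 3-month visit window is Day 76-104 (protocol 13.5; SAP 1).

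On timing of the test, SAP 1 states: "The hypothesis testing of the primary endpoints will be performed when all subjects complete their 3-month follow-up". SAP 7.5.1 names the measure a 3-month PAE rate, ties outcome determination to the 3-month follow-up and the protocol's PAE definition, and treats committee-adjudicated cases as final at the 3-Month CSR. Later changes in PAE data are summarised descriptively in the Final CSR, without a new test.

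**The concern.** The cut-off is Day 90, but a compliant scan may be taken up to Day 104. A silent stenosis has no observed onset; the scan is the first evidence of it. If the scan date were taken as the event date, a severe stenosis found on Day 91-104 would drop out of the primary count. That error runs one way: it can only lower the PAE rate set against the 12% goal. The endpoint drives the sample size and supports the CE-mark report, so a counting rule settled after cases are known would be unwelcome.

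A second, related worry is that the 3-month visit may fall on Day 76-89, before the 90-day window closes. Sites ask about adverse events at visits. The next visit is on Day 166-194, and subjects followed only to 3 months have none. The last days before Day 90 might therefore not have been asked about when the test is run.

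**Working it through.** **Inputs.** From the documents: 135 evaluable subjects; goal 12%; exact binomial test, one-sided 2.5%; 30 subset scans; scan window Day 76-104; PAE limit Day 90; PV stenosis under 1% with RF and none reported with pulsed field (protocol 5.4.1); enrolment 8-10 months. Assumed: severe-stenosis rate r of 0.1%, 0.5% or 1%; scans spread evenly over the window; for the worst case, the scan date governs. The assumed PAE rate and power behind 135 are blacked out, so that figure cannot be reproduced. The decision boundary can be.

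**Boundary.** Exact 97.5% upper limits at n = 135:
- 8 events: 11.34%, pass.
- 9 events: 12.28%, fail.
- Actual type I error: P(X ≤ 8 | 135, 0.12) = 1.46%.

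One late-scan case therefore changes the result only if exactly 8 other subjects have a PAE. For true PAE rates of 3-8%, the chance of a count of exactly 8 is 3-14%.

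**Share of the scan window past the limit.** Day 76-104 is 29 days and Day 91-104 is 14 days, so f = 14/29 = 0.483.

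**Effect if the scan date governs.** Expected missed cases are 30·r·f. The chance of at least one is 1 − (1 − r·f)^30. Type I error is recomputed at a counted rate of 0.12 − 30·r·f/135. The fail-to-pass chance is P(counted ≤ 8) − P(all ≤ 8). Here all events are binomial(135, p), and counted events are binomial(30, p − r·f) plus binomial(105, p), with p from 3% to 7%.

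| r | Expected missed | At least one | Type I error | Fail turned to pass |
|---|---|---|---|---|
| 0.1% | 0.014 | 1.4% | 1.47% | 0.04-0.21% |
| 0.5% | 0.072 | 7.0% | 1.53% | 0.21-1.04% |
| 1% | 0.145 | 13.5% | 1.60% | 0.40-2.08% |

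For r = 1%: 30 × 0.01 × 0.483 = 0.145; the counted rate is 0.12 − 0.145/135 = 0.1189; P(X ≤ 8) = 1.60%. Symptom-triggered scans in the other 105 subjects are not included.

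**Second worry.** I simulated 135 subjects, with enrolment uniform over 8 or 10 months and visits uniform in their windows. If the test were run on the day of the last 3-month visit, about 0.10 or 0.14 of a subject on average would not yet have reached Day 90. About 23 or 18 subjects would have been seen before Day 90 with their 6-month visit still ahead. The unasked days total about 169 or 137 of 135 × 83 = 11,205 days in Day 8-90, which is 1.5% or 1.2%. Data review and lock come before analysis (protocol 23.1.4). With a 30-day lag the 23 or 18 subjects become about 15 or 12, with 60 days about 7 or 5, and with 90 days about 0.5.

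**The case for a change.** The best argument for a change is that the authors aligned other rules with the visit window and not this one. Table 5 ties phrenic nerve paralysis to a test at the 3-month visit, so a Day 104 assessment counts. The SAP starts the drug-failure period at Day 105, the day after the window closes. SAP 7.5.1 points both to the 3-month follow-up and to a definition that ends at Day 90, which shows the tension without resolving it. The SAP is also a shade looser than the protocol on whether later stenosis, fistula and death count, and a sentence or cross-reference would cost little.

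The factual part stands: the two windows do not match, and no legible text dates a scan-detected stenosis. Three things weaken the inference.
- The bias needs scan dating, which nothing in the text adopts. The definitions turn on occurrence, protocol 14.3 on start dates, and the committee adjudicates; it can judge that a severe narrowing seen on Day 95 began before Day 90.
- A rule may already exist in the committee's charter or in blacked-out parts of SAP 7.1, 7.6.1 or 7.8.1. Its absence from the public copy is not evidence of a gap.
- The obvious remedy, counting every stenosis seen through Day 104 unless later onset is documented, would in effect move the limit to Day 104, because onset is not observed. That trades an undercount for an overcount and alters the primary endpoint.

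On the second worry, visits are not the only source of events. Subjects may report at any time (protocol 14.4.1), and PAEs and serious events are due within 72 hours of awareness (protocol Table 10). Death, fistula and severe stenosis are unlikely to wait for a routine question.

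**Conclusion.** No change to the plan is needed. This is missing detail that adjudication would ordinarily settle, and the conclusion of the safety test does not hang on it. On the least favourable reading, with a severe-stenosis rate of 1% (the ceiling of the protocol's RF figure for stenosis of any degree), fewer than 0.15 cases would be missed, type I error would stay at or below 1.60%, and the chance of a wrong pass would be at most about 2%. At 0.1% that chance is at most 0.21%. These figures rest on evenly spread scans and on scan dating, which the text does not favour.

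A late-scan case would not vanish either. Severe stenosis is reported as an adverse event (protocol 7.3.3), and the CT/MRA subset is summarised separately (SAP 7.12.3). SAP 8 lets the report describe supplementary analyses, so a sensible analyst would list such a case beside the primary count. The second worry touches about 1.5% of Day 8-90 follow-up at most, shrinks with any data lag, and is covered by expedited reporting and the descriptive update in the Final CSR. My view would change only if the committee's charter, or the blacked-out text, fixed the scan date as the event date and several late-scan stenoses then occurred.

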7.4.2 Primary Effectiveness Endpoint

The primary effectiveness endpoint (PEE) for a subject is acute procedural success, which is achieved by electrical isolation of clinically relevant targeted PVs (confirmed by entrance block) after adenosine/isoproterenol challenge at the end of the index ablation procedure (section 7.4.1 in the Protocol). Use of

a non-study device to achieve PVI is considered an acute procedural failure. The primary acute effectiveness success rate will be compared against a performance goal of 90%.

The hypotheses to be tested for this evaluation are:

$$H_0: P_E \leq 0.90 \text{ vs. } H_A: P_E > 0.90,$$

where P_E denotes the rate of acute procedure success.

7.4.3 Secondary Effectiveness Endpoint

The secondary effectiveness endpoint is 12-month effectiveness success, which is defined as freedom from documented (symptomatic and asymptomatic) atrial arrhythmia episodes including atrial fibrillation (AF), atrial tachycardia (AT), or atrial flutter (AFL, of unknown origin*). The AF/AT/AFL episodes will be assessed based on the electrocardiographic data (≥ 30 seconds on arrhythmia monitoring device) during the effectiveness evaluation period (91-365 days post the index procedure). Acute procedural failure (i.e., failure to achieve entrance block with the study device in any of the clinically relevant targeted PVs) will also be deemed a 12-month effectiveness failure. The secondary effectiveness success rate will be compared against a performance goal of 50%.

The hypotheses to be tested for this evaluation are:

$$H_0: P_{12m} \leq 0.50 \text{ vs. } H_A: P_{12m} > 0.50,$$

where P_{12m} denotes the proportion of subjects who are failure-free at 12 months follow-up.

**AFL of unknown origin is defined as all AFL except those CTI dependent AFL as confirmed by 12-lead electrocardiogram (ECG) or entrainment maneuvers in an EP study.*

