### **7.4.2 Secondary Hypothesized Endpoints**

#### **12-Month Effectiveness**

Freedom from documented (symptomatic and asymptomatic) atrial arrhythmia (AF, AT or AFL of unknown origin\*) episodes based on electrocardiographic data ( $\geq 30$  seconds on arrhythmia monitoring device) during the effectiveness evaluation period (day 91-day 365) on or off antiarrhythmic therapy. Acute procedural failure (i.e., failure to achieve entrance block with the study device in any of the clinically relevant targeted PVs) will also be deemed a 12-month effectiveness failure.

*\*AFL of unknown origin is defined as all AFL except those CTI dependent AFL as confirmed by 12-lead electrocardiogram (ECG) or entrainment maneuvers in an EP study.*

Further refer to Appendix 1 for definitions on effectiveness terms.

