7.5.2 Criteria for Study Success

The study will be considered a success if both primary safety and acute effectiveness endpoints are met based on the 3-month follow-up data.

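### Recurrences count only to Day 365, but the 12-month Holter is on time up to Day 379, so a late silent recurrence can be missed because of the appointment date (minor)

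*SAP*

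**What the plan says.** Both documents close the secondary endpoint at Day 365. SAP 7.4.3 counts episodes "during the effectiveness evaluation period (91-365 days post the index procedure"), and Protocol 7.4.2 counts them "during the effectiveness evaluation period (day 91-day 365) on or off antiarrhythmic therapy". Silent as well as symptomatic episodes are failures.

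Both documents let the 12-month visit run later. Protocol 13.5 sets the visits at "3 months (3M, day 76-104), 6 months (6M, day 166-194) and 12 months (12M, day 335-379"), and SAP section 1 has "12 months (Day 335-379) following the index ablation procedure (Day 0"). Protocol 13.5.2 ties the Holter to the visit: "per CIP a Holter monitor will be used at the 3-, 6- and 12-months follow-up visit". The readable text gives the 12-month Holter no separate window. Protocol section 16 treats a visit out of window as a deviation; Day 366-379 is inside the window, so a Holter on those days is not one.

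Between the 6-month visit and Day 365 the other scheduled rhythm-device recordings are remote transmissions of at least 30 seconds, "every month until the effectiveness evaluation period is completed (12 months post index ablation procedure"). Table 4, footnote 7, puts these "monthly as of 6-month follow-up visit and whenever subject feels symptoms".

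**The concern.** Take two subjects with the same silent AF burden late in the year. One has the Holter on Day 360 and can fail on it. The other attends on Day 372, which is equally compliant. On the readable text, nothing on that Holter counts, and no long recording was made in the window after the 6-month visit. Whether a silent recurrence before Day 366 is detected then depends partly on when the appointment fell.

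The direction is favourable to the device. An in-window recurrence that nothing records leaves the subject event-free at Day 365, which raises the Kaplan-Meier rate compared with 50%. At stake is a modest upward tilt in the hypothesis-tested secondary result. The primary endpoints are not involved.

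**Working it through.** **Day counts (from the visit windows and endpoint period)**

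- 12-month window: 379 - 335 + 1 = 45 days.
- After the endpoint closes: 379 - 366 + 1 = 14 days, and 14/45 = 31.1%.
- If the 24 hours must finish by Day 365, the Holter must be fitted on Day 335-364: 364 - 335 + 1 = 30 days. The other 15 of 45 (33.3%) are too late.
- Late attender's last scheduled in-window Holter: the 6-month one, Day 166-194. Gap to Day 365: 365 - 194 = 171 to 365 - 166 = 199 days.
- The 3-month Holter can precede Day 91: Day 76-90 is 15 of its 29 compliant days (76-104). Only the 6-month Holter is always inside the endpoint period.

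**Size (assumptions; none of f, y or S is in the documents)**

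- f = share of 12-month Holters done after Day 365. Visits spread evenly give f = 14/45 = 0.311.
- y = share of late, otherwise event-free subjects whose only recurrence appears on that Holter: 1-5%. It stands in for what a timely Holter would have shown. The two need not be equal, because an episode on Day 372 need not have been present on Day 360.
- S = success rate under the Day 365 cut: 60-70%.
- n = 135, no censoring.

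Shift in the rate = f × y × S:

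- Low: 0.311 × 0.01 × 0.60 = 0.0019, or 0.2 points; × 135 = 0.25 subjects.
- High: 0.311 × 0.05 × 0.70 = 0.0109, or 1.1 points; × 135 = 1.47 subjects.
- If only 10% are late: 0.10 × 0.01 × 0.60 = 0.0006 to 0.10 × 0.05 × 0.70 = 0.0035, or 0.06 to 0.35 points.
- If 50% are late: 0.50 × 0.01 × 0.60 = 0.0030 to 0.50 × 0.05 × 0.70 = 0.0175, or 0.3 to 1.75 points.

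**Could it change the secondary result? (illustration only)**

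The plan's own pass mark cannot be reproduced. The sample-size assumptions and the Per Protocol definition are redacted, and Protocol 19.8.3 censors some subjects. With n = 135 and no censoring, the lower two-sided 95% bounds are:

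- 78/135: plain Greenwood 0.4945 (fails).
- 79/135: plain 0.5021 (passes); log-log 0.4974 and exact 0.4973 (fail).
- 80/135: log-log 0.5048, exact 0.5047 (pass).

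The illustrative pass mark c is therefore 79 or 80. Let X ~ Binomial(135, S) be the successes under the Day 365 cut, and L ~ Binomial(X, f × y) those with a first recurrence only on a late Holter. The chance that the result passes with the cut but fails if those findings count is P(X ≥ c and X - L < c), with f = 0.311:

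| S | c = 79, y = 1% / 5% | c = 80, y = 1% / 5% |
|---|---|---|
| 60% | 1.6% / 8.4% | 1.7% / 8.7% |
| 65% | 0.5% / 3.1% | 0.7% / 4.0% |
| 70% | 0.03% / 0.2% | 0.06% / 0.4% |

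At S = 60% the Day 365 cut itself passes only 67% (c = 79) or 61% (c = 80) of the time. The mismatch matters only when the result is already close.

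**The case against.** The strongest reply is that nothing here is an error. Protocol and SAP agree on the endpoint period and on the visit window, and a window that extends past a fixed analysis time is not a contradiction. That stands: the point is about ascertainment, not about the endpoint definition.

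Several mitigations also stand. The 12-month window is lopsided in the right direction, with 30 days before Day 365 and 14 after, and Day 365 is the target, so fewer than 31% may attend late. Weekly transmissions run through month 5, monthly ones follow, and symptomatic subjects can transmit at any time. These narrow the gap, but symptom-triggered recordings do not reliably capture silent episodes, which the endpoint includes.

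It is also fair that counting findings through Day 379 measures something different. It gives late attenders up to 14 extra days at risk, so exposure again depends on the appointment, and it may charge episodes that began after Day 365. That estimate therefore cannot replace the planned one.

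A reader might infer two stronger points that the documents do not support:

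- **That the plan has no rule for late findings.** SAP 7.1 (general conventions), 7.8.3 (missing data) and 7.10 (secondary analysis, including its best- and worst-case scenarios) are partly or wholly redacted, and a rule may sit there.
- **That the trial's success is at risk.** SAP 7.5.2 says the study is "considered a success if both primary safety and acute effectiveness endpoints are met"; the 12-month result is not part of that criterion.

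**Conclusion.** The mismatch is real and appears in both documents, but it is minor. On 14 of 45 compliant days (15 if the recording must be complete by Day 365) the last Holter cannot contribute fully to the endpoint. A late attender may then have no in-window Holter after Day 166-194. The resulting loss of detection tends to favour success on the secondary endpoint.

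The size is unknown. With evenly spread visits, a 1-5% yield and 60-70% success, it is about 1 point or less. It would reach 1.75 points only if half the subjects attended late at the highest yield and success rate assumed. The 79-80 of 135 pass mark is illustrative and should not be read as the plan's threshold. The day counts are firm; the size rests wholly on assumptions.

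**What to change.** **Main change.** Keep the Day 365 cut as the tested estimate and leave the visit window alone. For any 12-month visits still to come, ask sites, where possible, to fit the Holter on Day 335-364 so that the 24 hours end by Day 365. This costs one message to sites. It helps only if such visits remain, which the documents do not show; the SAP's signature record is dated 2025.

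**Secondary change, unless redacted text already covers it.** In a SAP addendum written before the 12-month data are analysed, commit to reporting how many subjects had their 12-month Holter after Day 365, and how many of those had a first recurrence only on it. Optionally, add one supportive estimate to the list in SAP 7.10 that counts these subjects as failures at Day 365. Label it a lower bound that includes up to 14 extra days at risk, not a correction. The data are already being collected, and the hypothesis, alpha and test do not change.
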